1.2.5 Summary

This study represents an initial trial of examining the use of PSA-TRICOM in the neoadjuvant setting. Several characteristics of prostate cancer make it an ideal target for immunotherapy. Its relative indolence allows sufficient time to generate immune responses, which usually take weeks or months to mount. A randomized, controlled phase II PSA-TRICOM trial utilizing a poxvirus-based vaccine platform expressing PSA and 3 costimulatory molecules (B7.1, ICAM-1, and LFA-3) demonstrated a statistically significant improvement in overall survival in vaccine-treated patients for metastatic prostate cancer. The benefits of vaccine in the NCI study however were greatest in patients with lower tumor burden. Therefore, it would be rational to investigate the benefits of vaccines in patients with earlier stage of disease who have less tumor burden. The data gathered regarding immunologic response as well as serologic response will be invaluable in determination if larger studies to examine endpoints such as biochemical recurrence are warranted.

2 ELIGIBILITY ASSESSMENT AND ENROLLMENT

2.1 ELIGIBILITY CRITERIA

2.1.1 Inclusion Criteria

- 2.1.1.1** Patients must have histopathological documentation of adenocarcinoma of the prostate prior to starting this study and evaluable biopsy tissue (e.g., unstained slides or blocks) available for analysis. If evaluable tissue is not available, the patient must agree to undergo a pre-vaccination prostate biopsy on study as an alternative to having available tissue available.
- 2.1.1.2** Patients must be a surgical candidate for radical prostatectomy based on standard workup of PSA, biopsy results, and if necessary supplemental imaging.
- 2.1.1.3** Patients must have chosen radical prostatectomy as their definitive treatment of choice for management of their prostate cancer.
- 2.1.1.4** Patients must have a performance status of 0 to 1 according to the ECOG criteria (see [Appendix A](#)).
- 2.1.1.5** No systemic steroid or steroid eye drop use within 2 weeks prior to initiation of experimental therapy. Limited doses of systemic steroids to prevent IV contrast, allergic reaction or anaphylaxis (in patients who have known contrast allergies) are allowed.
- 2.1.1.6** Hematological eligibility parameters (within one month of starting therapy):
 - Granulocyte count $\geq 1,500/\text{mm}^3$
 - Platelet count $\geq 50,000/\text{mm}^3$
 - Hgb ≥ 8 g/dL

- 2.1.1.7** Biochemical eligibility parameters (within one month of starting therapy):
- a. Hepatic function: Bilirubin < 1.5 mg/dl (OR in patients with Gilbert's syndrome, a total bilirubin \leq 3.0 mg/dL), AST and ALT < 2.5 times upper limit of normal.
 - b. Creatinine \leq 1.5 X ULN
 - c. Patients must be test negative for HIV, Hepatitis B and C.
- 2.1.1.8** Patients must not have other active invasive malignancies within the past 2 years (with the exception of non-melanoma skin cancers) or life threatening illnesses.
- 2.1.1.9** Patients must be willing to travel to the study site for follow-up visits.
- 2.1.1.10** Patients must be \geq 18 years of age.
- 2.1.1.11** All patients who have received prior vaccination with vaccinia virus (for smallpox immunization) must not have a history of allergy to the vaccine.
- 2.1.1.12** Patients must understand and sign informed consent that explains the neoplastic nature of their disease, the procedures to be followed, the experimental nature of the treatment, alternative treatments, potential risks and toxicities, and the voluntary nature of participation.
- 2.1.1.13** The effects of the study agents used in this protocol on the developing human fetus are unknown. For this reason men must agree to use adequate contraception (abstinence, vasectomy, or female partner use of intrauterine device (IUD), hormonal [birth control pills, injections, or implants], tubal ligation) prior to study entry and for up to one month after the last vaccination.
- 2.1.2** *Exclusion Criteria*
- 2.1.2.1** Prior splenectomy.
- 2.1.2.2** The recombinant vaccinia vaccine should not be administered if the following apply to either recipients or, for at least 3 weeks after vaccination, their close household contacts (Close household contacts are those who share housing or have close physical contact):
- persons with active or a history of eczema or other eczematoid skin disorders
 - those with other acute, chronic or exfoliative skin conditions (e.g., atopic dermatitis, burns, impetigo, varicella zoster, severe acne or other open rashes or wounds) until condition resolves
 - pregnant or nursing women; children under 3 years of age
 - Patients should have no evidence, as listed below, of being immunocompromised:
 - HIV positivity due to the potential for decreased tolerance and risk for severe side effects.
 - Hepatitis B or C positivity.
 - Concurrent use of topical steroids (including steroid eye drops) or systemic steroids. This is to avoid immunosuppression which may lead to potential complications with vaccinia (priming vaccination). Nasal or inhaled steroid use is permitted.

2.1.2.3 Patients with known allergy to eggs.

2.1.2.4 Other serious intercurrent illness.

2.1.2.5 Patients with a history of unstable or newly diagnosed angina pectoris, recent myocardial infarction (within 6 months of enrollment) or New York Heart Association class II–IV congestive heart failure.

2.1.2.6 Patients with significant autoimmune disease that is active or potentially life threatening if activated.

2.1.2.7 Patients with clinically significant cardiomyopathy requiring treatment.

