3 STUDY IMPLEMENTATION

3.1 STUDY DESIGN

This is a Phase II study in which a maximum of 27 patients will be enrolled. Patients with clinically localized prostate cancer will be enrolled and treated with rV-PSA(L155)-TRICOM (PROSTVAC-V/TRICOM) followed by the rFowlpox-PSA (L155)-TRICOM (PROSTVAC-F/TRICOM) boost monthly until they have had radical prostatectomy or meet off therapy criteria as listed in section 3.7.1. At week 10 (plus up to 3 months) the patients will undergo a radical prostatectomy at the NIH Clinical Center by open or robotic-assisted laparoscopic approach as deemed appropriate by the surgeon. We will continue to follow for safety, and immunologic data.

Schedule

Week 1	Week 3 or 5 ^{1,3}	Week 5 or 9 ^{1,3}	Week 9 or 13 ^{1,3}	Week 10 ^{2,3}
Priming Vaccination	Booster Vaccination	Booster Vaccination	Booster Vaccination	Radical Prostatectomy

¹Please note that above dates may be +/- 1 week to accommodate for scheduling

²Please note the date of radical prostatectomy may be within three months after week 10 to accommodate for scheduling and any reasonable delays due to clinical preoperative considerations. Patients with delay of greater than one month may receive additional monthly booster vaccines. If feasible, surgery should be scheduled within 7-14 days after the final booster.

³Patients who were enrolled prior to Amendment B will continue to follow the original week 5, 9 and 13 dosing schedule. However, surgery on these patients can be performed 7-14 days after the last vaccine is given.

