7.3.1 Reporting Pregnancy

7.3.1.1 Paternal exposure

Male patients should refrain from fathering a child or donating sperm during the study and for one month after the last dose of PROSTVAC. Pregnancy of the patient's partner is not considered to be an AE. However, the outcome of all pregnancies (spontaneous miscarriage, elective termination, ectopic pregnancy, normal birth, or congenital abnormality) occurring from the date of the first dose until one month after the last dose should, if possible, be followed up and documented.

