11.1.9 Patient Care Implications and Contraindications

Cover vaccination sites with a sterile dry dressing (e.g., Telfa pad). Once the injection site is healed, no further barrier is necessary. As a precaution, protect injection sites that are exhibiting evidence of weeping, oozing or ulceration with a sterile dry dressing. In these circumstances, instruct patients to avoid direct contact of the injection site with susceptible individuals (e.g.; those who may be immunocompromised by disease or therapy). Instruct patients to avoid fathering a child for at least 4 months following therapy completion with the recombinant vaccine. Instruct patients receiving fowlpox vaccines to avoid direct contact with pet birds for at least 72 hours after vaccination or while there are any visible lesions at the injection site.

Due to the method of manufacturing (virus grown in primary chicken embryo dermal cells), patients with a history of allergy to eggs or egg products should not receive the vaccine.

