11.2.10.1 Patient Care Implications and Contraindications

Cover vaccination sites with a sterile dry dressing (e.g., Telfa pad). Instruct patients on proper hand-hygiene, sterile dressing care, bathing, laundering of clothing, *etc.* Treat patient bandages or dressings removed from the vaccination site as infectious waste and dispose in appropriate biohazard containers. Do not administer the recombinant vaccinia vaccine if the recipient, or for at least three weeks after vaccination, their close household contacts (close household contacts are those who share housing or have close physical contact):

- have active eczema or a history of eczema or atopic dermatitis, or Darier's disease.
- have other acute, chronic, or exfoliative skin conditions (*e.g.*, burns, impetigo, varicella zoster, severe acne, contact dermatitis, psoriasis, herpes or other open rashes or wounds), until the condition resolves.
- are pregnant or intend to become pregnant (due to the potential risk of fetal vaccinia); or are breast-feeding (due to the potential risk of contact transmission and inadvertent inoculation). It is currently unknown if vaccinia virus or antibodies are excreted in breast milk. Patients (*i.e.*, vaccinees) should avoid fathering a child for at least 4 months following completion of therapy with the recombinant vaccine.
- are in close contact with children less than 3 years of age (due to the potential risk of contact transmission and inadvertent inoculation).
- are immunodeficient or immunocompromised (by disease or therapy), including individuals with HIV infection.

Additionally, do not administer the recombinant vaccinia vaccine if the vaccinee:

- has a moderate or severe acute illness, until the illness resolves.
- is undergoing topical steroid therapy for inflammatory eye diseases, or undergoing therapy with systemic steroids; potential immune suppression increases risk for vaccinia-related complications.
- At this time, until a more definitive causal relationship is determined, it is recommended that patients with known CHF or clinically significant cardiomyopathy, not be vaccinated with recombinant vaccinia-based vaccines, due to the potential for development of myocarditis and/or pericarditis.

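### Sections 2.1.1.13 and 7.3.1.1 set contraception and no fathering at one month after the last vaccine, while 11.1.9 and 11.2.10.1 say at least 4 months; the periods should be aligned.

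*Combined protocol and SAP*

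**What the plan says.** Four places in the current protocol set a period after vaccination during which men should not father a child.

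- **2.1.1.13 (inclusion criterion).** Men must agree to adequate contraception "prior to study entry and for up to one month after the last vaccination". The reason given is that "The effects of the study agents used in this protocol on the developing human fetus are unknown".
- **7.3.1.1 (in the part on pregnancy reports).** "Male patients should refrain from fathering a child or donating sperm during the study and for one month after the last dose of PROSTVAC". The same section follows up partner pregnancies "occurring from the date of the first dose until one month after the last dose should, if possible, be followed up and documented".
- **11.1.9 (fowlpox product).** "Instruct patients to avoid fathering a child for at least 4 months following therapy completion with the recombinant vaccine".
- **11.2.10.1 (vaccinia product).** Vaccinees "should avoid fathering a child for at least 4 months following completion of therapy with the recombinant vaccine".

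Three design features decide who is affected.

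- **Boosting.** Section 3.1 has men receive the fowlpox "boost monthly until they have had radical prostatectomy or meet off therapy criteria as listed in section 3.7.1". Note 2 to its schedule is weaker: men delayed by more than one month may be given extra boosters.
- **Timing of surgery.** It is planned for week 10, if feasible 7 to 14 days after the final booster, but "the date of radical prostatectomy may be within three months after week 10".
- **Men who stop before surgery.** Under 3.8, those taken off vaccine for a 3.7.1 reason have a safety visit 4 to 5 weeks after the last dose. No further safety follow-up is required unless a grade 3 or higher event is unresolved.

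**The concern.** 2.1.1.13 is what a man agrees to at entry, and registration under 2.3 works from an eligibility checklist. It reads as a ceiling of one month. The product sections read as a floor of 4 months for the same agents. No supplied text says which governs or gives a reason for either length.

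A man held only to the criterion is released before the product text allows. The protocol justifies the restriction by unknown fetal risk, so ending it earlier than its own product instructions needs a stated reason. What is at stake is possible exposure of a partner's pregnancy during the difference between the two periods. No study result is at stake.

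**Working it through.** The plan gives no calculated figure to reproduce. The check compares the texts and then asks which men the difference reaches.

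**1. Size of the wording gap**

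| Section | What it restricts | Period | Counted from |
|---|---|---|---|
| 2.1.1.13 | Contraception | Up to 1 month | Last vaccination |
| 7.3.1.1 | Fathering, sperm donation | Study period and 1 month | Last dose |
| 11.1.9 | Fathering | At least 4 months | End of fowlpox therapy |
| 11.2.10.1 | Fathering | At least 4 months | End of vaccinia therapy |

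Difference: 4 − 1 = 3 months. Fowlpox is the last product given, so the 11.1.9 clock starts at the same dose as the one-month clock, and the full 3 months applies on paper.

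**2. Does the vaccinia clock remove the conflict?** Vaccinia is given once, at week 1 (3.2.1), so 11.2.10.1 could be counted from that dose. One month is 365.25/12/7 = 4.35 weeks, and four months is 17.39 weeks.

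- Vaccinia period ends: 1 + 17.39 = week 18.39.
- One-month rule, last booster week 9: 9 + 4.35 = week 13.35.
- One-month rule, last booster week 13 (enrolled before Amendment B): 13 + 4.35 = week 17.35.

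At nominal visit weeks the vaccinia period still ends later, though only by about a week on the older schedule. This reading narrows the 11.2.10.1 gap and leaves 11.1.9 untouched.

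**3. Who is reached in practice**

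- *Surgery on schedule.* Surgery falls 7 to 14 days after the last booster, inside the one month. If natural conception is not possible after prostatectomy, the practical gap is nil.
- *Surgery delayed, boosters continued monthly.* Each booster restarts the one-month clock, so little or nothing is uncovered before surgery.
- *Surgery delayed, no extra boosters.* The one month can run out before surgery. The in-study phrase in 7.3.1.1 would still cover these men; 2.1.1.13 has no such phrase.
- *Vaccine stopped before surgery.* After the safety visit at 4 to 5 weeks a man may go off study (3.7.2, item 1). The study period and the one month then end at about the same time, leaving up to about 3 months of the section 11 period.

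**4. Limits on the last group.** The 3 months is an upper limit. A man removed because toxicity has persisted beyond 42 days has already used part of the 4 months and goes directly to definitive therapy (3.3). A man removed because surgery slipped by more than 3 months has, without extra boosters, used most of it.

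**The case against.** The strongest reply is that the protocol already gives the safer instruction. 11.1.9 directly orders staff to instruct patients on 4 months, and applying the longer period satisfies every section. This stands in part: it would be wrong to infer that staff are told nothing about 4 months. But the criterion a man accepts at entry still says one month, and no text says that section 11 overrides it.

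Second, 7.3.1.1 also covers the study period, and 3.8 schedules visits to 12 to 15 months after surgery. Read naturally, it already exceeds 4 months for operated men. That is fair for 7.3.1.1. It does not help 2.1.1.13, or men who leave the study soon after a safety visit.

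Third, sections 11.2.9 and 11.2.11 use an interval of four weeks, which might seem to support one month. Those passages concern healthcare workers or their household contacts who intend pregnancy, and vaccination during or shortly before pregnancy. They set no rule for male vaccinees, and the same vaccinia section tells male vaccinees 4 months.

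Fourth, the consent form and most of the patient instruction sheet are not in the copy reviewed, so what patients are actually told is unknown. This is correct. The point is therefore limited to the protocol text; the documents do not support a claim that patients receive the wrong advice.

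**Conclusion.** The inconsistency is real and minor. Two sections say one month, two say at least 4 months, and the documents do not reconcile them. The practical gap is up to about 3 months, mainly for men who stop vaccine before surgery or wait for delayed surgery without extra boosters. The documents do not give their number; it is probably small.

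This rests on two assumptions: that natural conception is not possible after prostatectomy, and that the 4 months is counted from the last fowlpox dose.

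Two stronger readings should be resisted. A reader might infer that every enrolled man is exposed for the whole 3 months; the planned timing of surgery rules that out under the first assumption. A reader might also infer that the one-month pregnancy follow-up window contradicts section 11, but section 11 sets no follow-up period, so extending that window is a judgement and not the correction of a conflict.

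Endpoint, sample size and analysis are unaffected.

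**What to change.** Change the end of 2.1.1.13 to: *for at least 4 months after the last vaccination*. Change the fathering and sperm-donation period in 7.3.1.1 to: *during the study and for at least 4 months after the last dose*. If the sponsor has a documented reason for one month, change 11.1.9 and 11.2.10.1 instead, so that one period appears throughout. Bring the consent text into line if it also says one month.

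The cost is one wording amendment, up to 3 more months of contraception for the men concerned, and possible re-consent of men already enrolled, for which 10.6.1 provides a telephone route. Lengthening the partner-pregnancy follow-up window is a separate, optional decision; for men with no visit after 4 to 5 weeks it would capture little without some further contact.

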2.2 RESEARCH ELIGIBILITY EVALUATION

- History and Physical Exam (within 1 month prior to enrollment)
- Performance Status Evaluation (within 1 month prior to enrollment)
- Pathologic Confirmation of Diagnosis. Patients that do not have previously collected biopsy material available will be asked to undergo a prostate biopsy.
- EKG
- Laboratory Evaluation (within 1 month prior to enrollment)
 - CBC with differential and platelet count
 - Acute care panel
 - Hepatic Panel
 - HIV serology
 - Hepatitis panel

2.3 REGISTRATION PROCEDURES

Authorized staff must register an eligible candidate with NCI Central Registration Office (CRO) within 24 hours of signing consent. A registration Eligibility Checklist from the web site (<http://home.ccr.cancer.gov/intra/eligibility/welcome.htm>) must be completed and sent via encrypted email to: NCI Central Registration Office (HOIS) [contact]. After confirmation of eligibility at Central Registration Office, CRO staff will call pharmacy to advise them of the acceptance of the patient on the protocol prior to the release of any investigational agents. Verification of Registration will be forwarded electronically via e-mail to the research team. A recorder is available during non-working hours.

2.4 BASELINE STUDIES (WITHIN 4 MONTHS PRIOR TO TREATMENT)

Baseline examinations need not be repeated if they have been performed within the appropriate time frame.

- History and Physical Exam
- HLA class 1 profile
- Serum PSA (tumor marker)

- CBC
- BUN, Creatinine
- ALT, AST, Total bilirubin
- Lymphocyte Phenotyping (TBNK)
- Research Studies (See section 5 for details)
 - MRI prostate¹ (can be obtained within one year prior to treatment)
 - Immunology assays (including immune T-cell response assay, CD3, 4, 8 subsets and CD4:CD8 ratio, Class II immune responses, CTL assay, TBNK, and sera antibody analyses)
 - Prostate biopsy (performed only if previously collected tissue is not available. If biopsy was performed at screening, leftover material may be used for research study.)

¹ MRI of the prostate is strongly encouraged and will be performed prior to and after vaccination course if logistically feasible.

3 STUDY IMPLEMENTATION

3.1 STUDY DESIGN

This is a Phase II study in which a maximum of 27 patients will be enrolled. Patients with clinically localized prostate cancer will be enrolled and treated with rV-PSA(L155)-TRICOM (PROSTVAC-V/TRICOM) followed by the rFowlpox-PSA (L155)-TRICOM (PROSTVAC-F/TRICOM) boost monthly until they have had radical prostatectomy or meet off therapy criteria as listed in section 3.7.1. At week 10 (plus up to 3 months) the patients will undergo a radical prostatectomy at the NIH Clinical Center by open or robotic-assisted laparoscopic approach as deemed appropriate by the surgeon. We will continue to follow for safety, and immunologic data.

Schedule

Week 1	Week 3 or 5 ^{1,3}	Week 5 or 9 ^{1,3}	Week 9 or 13 ^{1,3}	Week 10 ^{2,3}
Priming Vaccination	Booster Vaccination	Booster Vaccination	Booster Vaccination	Radical Prostatectomy

¹Please note that above dates may be +/- 1 week to accommodate for scheduling

²Please note the date of radical prostatectomy may be within three months after week 10 to accommodate for scheduling and any reasonable delays due to clinical preoperative considerations. Patients with delay of greater than one month may receive additional monthly booster vaccines. If feasible, surgery should be scheduled within 7-14 days after the final booster.

³Patients who were enrolled prior to Amendment B will continue to follow the original week 5, 9 and 13 dosing schedule. However, surgery on these patients can be performed 7-14 days after the last vaccine is given.

3.2 DRUG ADMINISTRATION

3.2.1 Study drugs

Study drugs will be prepared and placed in syringes by the Clinical Center Pharmacy personnel. Both vaccines are given subcutaneously. (See sections 11.1.3 and 11.2.3 for preparation instructions.)

Week 1	rV-PSA(L155)-TRICOM	2 x 10 ⁸ infectious units s.c.
Monthly booster	rF-PSA(L155)-TRICOM	1 x 10 ⁹ infectious units s.c.

3.2.2 Precautions

- Prior to administration of the drugs, safe handling precautions should be thoroughly reviewed (see sections 11.1.7 and 11.2.7 in “Pharmaceutical Information”).
- The proper procedure for disposing the live vaccine is a critical part of drug administration (see sections 11.1.8 and 11.2.8 in “Pharmaceutical Information”).
- Patients must have a copy of the “Patient Education Sheet” (see Appendix B)

3.3 TREATMENT MODIFICATIONS

Patients must have recovered to ≤ grade 1 attributable toxicity for the parameters used to assess levels of organ function required for eligibility (see section 2.1) after each vaccination in order to receive a subsequent vaccination. If > grade 2 attributable toxicity persists for > 42 days, the patient will not receive further vaccine inoculations and will be removed from protocol and proceed directly to definitive therapy. Assessments will be performed during each vaccination and blood draw interval for immunologic testing as described in section 3.4.1.3.

